#### **6.6.1.1. Dose modification and toxicity management of infusion-reactions related to pembrolizumab**

Pembrolizumab may cause severe or life-threatening infusion-reactions including severe hypersensitivity or anaphylaxis. Signs and symptoms usually develop during or shortly after drug infusion and generally resolve completely within 24 hours of completion of infusion. Dose modification and toxicity management guidelines on pembrolizumab associated infusion reaction are provided in the table below.

**Pembrolizumab Infusion-Related Reaction Dose Modification and Treatment Guidelines**

NCI CTCAE Grade	Treatment	Premedication at Subsequent Dosing

Grade 1 Mild reaction; infusion interruption not indicated; intervention not indicated.
	
Increase monitoring of vital signs as medically indicated until the participant is deemed medically stable in the opinion of the investigator.
	
None

Grade 2 Requires therapy or infusion interruption but responds promptly to symptomatic treatment (e.g., antihistamines, NSAIDs, narcotics, IV fluids); prophylactic medications indicated for ≤24 hrs.
	
Stop Infusion. Additional appropriate medical therapy may include but is not limited to:
 
 
• IV fluids
 
• Antihistamines
 
• NSAIDs
 
• Acetaminophen
 
• Narcotics
 
 
Increase monitoring of vital signs as medically indicated until the participant is deemed medically stable in the opinion of the investigator. If symptoms resolve within 1 hour of stopping drug infusion, the infusion may be restarted at 50% of the original infusion rate (e.g. from 100 mL/hr. to 50 mL/hr.). Otherwise dosing will be held until symptoms resolve and the participant should be premedicated for the next scheduled dose. Participants who develop Grade 2 toxicity despite adequate premedication should be permanently discontinued from further study drug treatment.
	
Participant may be premedicated 1.5 hrs (±30 minutes) prior to infusion of pembrolizumab with:
 
 
• Diphenhydramine 50 mg po (or equivalent dose of antihistamine).
 
• Acetaminophen 500 to 1000 mg po (or equivalent dose of analgesic).
 

Grades 3 or 4 Grade 3: Prolonged (i.e., not rapidly responsive to symptomatic medication and/or brief interruption of infusion); recurrence of symptoms following initial improvement;
	
Stop Infusion. Additional appropriate medical therapy may include but is not limited to:
 
 
• Epinephrine**
 
• IV fluids
 
• Antihistamines
 
• NSAIDs
 
• Acetaminophen
 
• Narcotics
 
• Oxygen
 
• Pressors
 
	
No subsequent dosing

NCI CTCAE Grade	Treatment	Premedication at Subsequent Dosing
hospitalization indicated for other clinical sequelae (e.g., renal impairment, pulmonary infiltrates)  Grade 4: Life-threatening; pressor or ventilator support indicated	
 
• Corticosteroids
 
 Increase monitoring of vital signs as medically indicated until the participant is deemed medically stable in the opinion of the investigator. Hospitalization may be indicated. **In cases of anaphylaxis, epinephrine should be used immediately. Participant is permanently discontinued from further study drug treatment.	
Appropriate resuscitation equipment should be available at the bedside and a physician readily available during the period of drug administration. For further information, please refer to the Common Terminology Criteria for Adverse Events v4.0 (CTCAE) at http://ctep.cancer.gov		

Abbreviations: IV = intravenous; NSAID = non-steroidal anti-inflammatory drug; po = by mouth

**6.6.2. Dose Modification and Toxicity Management for Immune-Related AEs Associated with LY3475070 and/or in Combination with Pembrolizumab**

An immune-related AE (irAE) may be defined as an AE consistent with an immune-mediated chronic inflammatory reaction associated with drug exposure. These irAEs may occur shortly after the first dose or several months after the last dose of drug and may affect more than one body system simultaneously. Therefore, early recognition and initiation of treatment is critical to reduce complications. Based on existing clinical study data of immune checkpoint inhibitors, most irAEs are reversible and can be managed with interruptions of therapy, administration of corticosteroids and/or other supportive care. For suspected irAEs, ensure adequate evaluation to confirm etiology or exclude other causes. Additional procedures or tests such as bronchoscopy, endoscopy, skin biopsy may be included as part of the evaluation. Based on the severity of irAEs, withhold or permanently discontinue therapy and administer corticosteroids. Dose modification and toxicity management guidelines for potential irAEs are provided in the table below.

**Dose Modification and Toxicity Management Guidelines for Immune-related AEs Associated with Study Treatment**

## General Instructions:

1. Severe and life-threatening irAEs should be treated with IV corticosteroids followed by oral steroids. Other immunosuppressive treatment should begin if the irAEs are not controlled by corticosteroids.
2. Pembrolizumab must be permanently discontinued if the irAE does not resolve or the corticosteroid dose is not  $\leq 10$  mg/day within 12 weeks of the last pembrolizumab treatment.
3. The corticosteroid taper should begin when the irAE is  $\leq$  Grade 1 and continue at least 4 weeks.
4. If pembrolizumab has been withheld, pembrolizumab may resume after the irAE decreased to  $\leq$  Grade 1 after corticosteroid taper.

irAEs	Toxicity grade (CTCAE V5.0)	Action with pembrolizumab and LY3475070	Corticosteroid and/or other therapies	Monitoring and follow-up
Pneumonitis	Grade 2	Withhold	
 
Administer corticosteroids (initial dose of 1 to 2 mg/kg prednisone or equivalent) followed by taper
 
Add prophylactic antibiotics for opportunistic infections
 
	
 
Monitor participants for signs and symptoms of pneumonitis
 
Evaluate participants with suspected pneumonitis with radiographic imaging and initiate corticosteroid treatment
 

	Recurrent Grade 2, Grade 3, or 4	Permanently discontinue		
Diarrhea / Colitis	Grade 2 or 3	Withhold	
 
Administer corticosteroids (initial dose of 1 to 2 mg/kg prednisone or equivalent) followed by taper
 
	
 
Monitor participants for signs and symptoms of enterocolitis (i.e., diarrhea, abdominal pain, blood, or mucus in stool with or without fever) and of bowel perforation (i.e., peritoneal signs and ileus)
 
Participants with <math>\geq</math>Grade 2 diarrhea suspecting colitis should consider GI consultation and performing endoscopy to rule out colitis
 
Participants with diarrhea/colitis should be advised to drink liberal quantities of clear fluids. If sufficient oral fluid intake is not feasible, fluid and electrolytes should be substituted via IV infusion
 

	Recurrent Grade 3 or Grade 4	Permanently discontinue		
AST or ALT elevation or Increased Bilirubin	Grade 2 a	Withhold	
 
Administer corticosteroids (initial dose of 0.5 to 1 mg/kg prednisone or equivalent) followed by taper
 
	
 
Monitor with liver function tests (consider weekly or more frequently until liver enzyme value returned to baseline or is stable)
 

	Grade 3 b or 4 c	Permanently discontinue	
 
Administer corticosteroids (initial dose of 1 to 2 mg/kg prednisone or equivalent)
 
	

irAEs	Toxicity grade (CTCAE V5.0)	Action with pembrolizumab and LY3475070	Corticosteroid and/or other therapies	Monitoring and follow-up
			followed by taper	
Type 1 diabetes mellitus (T1DM) or Hyperglycemia	New onset T1DM or Grade 3 or 4 hyperglycemia associated with evidence of $\beta$ -cell failure	Withhold d	
 
Initiate insulin replacement therapy for participants with T1DM
 
Administer antihyperglycemic in participants with hyperglycemia
 
	
 
Monitor participants for hyperglycemia or other signs and symptoms of diabetes
 

Hypophysitis	Grade 2	Withhold	
 
Administer corticosteroids and initiate hormonal replacements as clinically indicated
 
	
 
Monitor for signs and symptoms of hypophysitis (including hypopituitarism and adrenal insufficiency)
 

	Grade 3 or 4	Withhold or permanently discontinue d		
Hyperthyroidism	Grade 2	Continue	
 
Treat with nonselective beta-blockers (eg, propranolol) or thionamides as appropriate
 
	
 
Monitor for signs and symptoms of thyroid disorders
 

	Grade 3 or 4	Withhold or permanently discontinue d		
Hypothyroidism	Grade 2, 3, 4	Continue	
 
Initiate thyroid replacement hormones (eg, levothyroxine or liothyronine) per standard of care
 
	
 
Monitor for signs and symptoms of thyroid disorders
 

Nephritis: grading according to increased creatinine or acute kidney injury	Grade 2	Withhold	
 
Administer corticosteroids (prednisone 1 to 2 mg/kg or equivalent) followed by taper
 
	
 
Monitor changes of renal function
 

	Grade 3 or 4	Permanently discontinue		

irAEs	Toxicity grade (CTCAE V5.0)	Action with pembrolizumab and LY3475070	Corticosteroid and/or other therapies	Monitoring and follow-up
Myocarditis	Grade 1 or 2	Withhold	
 
Based on severity of AE administer corticosteroids
 
	
 
Ensure adequate evaluation to confirm etiology and/or exclude other causes
 

	Grade 3 or 4	Permanently discontinue		
All Other immune-related AEs	Persistent Grade 2	Withhold	
 
Based on severity of AE administer corticosteroids
 
	
 
Ensure adequate evaluation to confirm etiology or exclude other causes
 

	Grade 3	Withhold or discontinue based on the event e		
	Recurrent Grade 3 or Grade 4	Permanently discontinue		

a AST/ALT: >3.0 to 5.0 x ULN if baseline normal; >3.0 to 5.0 x baseline, if baseline abnormal; bilirubin: >1.5 to 3.0 x ULN if baseline normal; >1.5 to 3.0 x baseline if baseline abnormal

b AST/ALT: >5.0 to 20.0 x ULN, if baseline normal; >5.0 to 20.0 x baseline, if baseline abnormal; bilirubin: >3.0 to 10.0 x ULN if baseline normal; >3.0 to 10.0 x baseline if baseline abnormal

c AST/ALT: >20.0 x ULN, if baseline normal; >20.0 x baseline, if baseline abnormal; bilirubin: >10.0 x ULN if baseline normal; >10.0 x baseline if baseline abnormal

d The decision to withhold or permanently discontinue pembrolizumab is at the discretion of the investigator or treating physician. If control achieved or ≤ Grade 2, pembrolizumab may be resumed.

e Events that require discontinuation include but are not limited to: Guillain-Barre Syndrome, encephalitis, Stevens-Johnson Syndrome, and toxic epidermal necrolysis.

Abbreviations: AE = adverse event; ALT = alanine aminotransferase; AST = aspartate transaminase; GI = gastrointestinal; irAE = immune-related adverse event; IV = intravenous; ULN = upper limit of normal

NOTE: The frequency or severity of known potential irAEs with pembrolizumab may be increased in combination with LY3475070. Therefore, particularly close monitoring for irAEs should be standard. For all irAEs of grade 2 or above would consider specialist consultation and/or additional work-up including labs and biopsy to confirm diagnosis. For certain toxicities of more serious clinical consequence, such as myocarditis, neurologic, or ophthalmologic irAE, consider withholding therapy for grade 2 toxicities and early hospitalization for close monitoring for grade 3 toxicities. For any grade 2 or greater suspected irAE, please consult with Lilly CRS/CRP.

For any other dose modifications, toxicities, or infusion-related reactions related to pembrolizumab, please consult the product label.

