## 8. Study Assessments and Procedures

- Study procedures and their timing are summarized in the SoA (Section 1.3). Protocol waivers or exemptions are not allowed.
- Immediate safety concerns should be discussed with the sponsor immediately upon occurrence or awareness to determine if the participant should continue or discontinue study intervention.
- Adherence to the study design requirements, including those specified in the SoA (Section 1.3), is essential and required for study conduct.
- All screening evaluations must be completed and reviewed to confirm that potential participants meet all eligibility criteria. The investigator will maintain a screening log to record details of all participants screened and to confirm eligibility or record reasons for screening failure, as applicable.
- Procedures conducted as part of the participant's routine clinical management (e.g., blood count) and obtained before signing of the ICF may be utilized for screening or baseline purposes provided the procedures met the protocol-specified criteria and were performed within the time frame defined in the SoA (Section 1.3).

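### Protocol Section 6.6.2 gives two different instructions for Grade 2 myocarditis: the irAE table says to withhold both drugs, the Note after it says only to consider it

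*Protocol*

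**What the plan says.** Protocol Section 6.6.2 has three parts that bear on this point.

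- **Lead-in.** The text before the table is directive: "Based on the severity of irAEs, withhold or permanently discontinue therapy and administer corticosteroids". It then introduces the table as the guidelines for dose modification and toxicity management.
- **Table.** The action column is headed "Action with pembrolizumab and LY3475070", so each entry applies to both drugs. The myocarditis row says to withhold at Grade 1 or 2 and to discontinue permanently at Grade 3 or 4. Neurologic and ophthalmologic irAEs have no row of their own and fall under the row for all other irAEs, which says to withhold at "Persistent Grade 2". Footnote d gives discretion: "The decision to withhold or permanently discontinue pembrolizumab is at the discretion of the investigator or treating physician". It is attached to type 1 diabetes/hyperglycemia, to Grade 3 or 4 hypophysitis and to Grade 3 or 4 hyperthyroidism. It is not attached to the myocarditis row or to the all-other row.
- **Note.** After warning that the combination may make irAEs more frequent or more severe, the Note says: "Therefore, particularly close monitoring for irAEs should be standard". It then says: "For certain toxicities of more serious clinical consequence, such as myocarditis, neurologic, or ophthalmologic irAE, consider withholding therapy for grade 2 toxicities". For Grade 3 it asks sites to consider early hospitalization. It also says: "For any grade 2 or greater suspected irAE, please consult with Lilly CRS/CRP".

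The SAP does not address irAE management.

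**The concern.** For Grade 2 myocarditis the table and the Note cover the same event, the same grade and the same treatment. One tells the site to stop dosing and the other tells it to think about stopping. A site that withholds satisfies both. A site that considers a hold, decides against it and keeps dosing has followed the Note but departed from the table.

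The softer wording falls on an event that the protocol treats as serious elsewhere. Exclusion criterion 15 bars patients whose prior immunotherapy caused a serious cardiovascular irAE of any grade and gives myocarditis as the example. Protocol Section 2.3 relies on clear irAE dose modifications as part of the benefit/risk case for the combination. A Note written for the more serious toxicities should not read as less strict than the table it follows.

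**Working it through.** No arithmetic applies. The check sets the table and the Note side by side, grade by grade, and then looks for any text that settles a difference.

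**Step 1. Compare the instructions.**

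| Event and state | Table | Note | Result |
|---|---|---|---|
| Myocarditis, Grade 1 | Withhold | Silent | No conflict |
| Myocarditis, Grade 2 | Withhold | Consider withholding | Differ; table stricter |
| Myocarditis, Grade 3 | Discontinue permanently | Consider early hospitalization | Compatible |
| Myocarditis, Grade 4 | Discontinue permanently | Silent | No conflict |
| Neurologic or ophthalmologic, Grade 2 not persistent | No action listed | Consider withholding | Note adds caution |
| Neurologic or ophthalmologic, Grade 2 persistent | Withhold (all-other row) | Consider withholding | Overlap; table stricter |
| Neurologic or ophthalmologic, Grade 3 | Withhold or discontinue, by event | Consider early hospitalization | Compatible |
| Neurologic or ophthalmologic, Grade 4 | Discontinue permanently | Silent | No conflict |

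Placing neurologic events in the all-other row has support in the table itself: footnote e, attached to the Grade 3 entry of that row, lists Guillain-Barré syndrome and encephalitis. Ophthalmologic events go there because no other row fits.

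**Step 2. Ask whether the Note can be purely additive.** For neurologic and ophthalmologic events that are Grade 2 but not persistent, it is: the table lists no action and the Note supplies one. For myocarditis it cannot be, because the table already holds both drugs from Grade 1. At Grade 2 the Note can only repeat the table or weaken it, and its verb is weaker.

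**Step 3. Look for a rule that decides between them.**

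- The lead-in agrees with the table but does not say that the table prevails over the Note.
- Footnote d shows that the protocol grants discretion explicitly where it wants to. Its absence from the myocarditis row suggests that none was intended, but that is an inference.
- The request to consult the sponsor physician does not say which text governs, nor what to do with dosing in the meantime.
- Protocol Section 8 says: "Immediate safety concerns should be discussed with the sponsor immediately upon occurrence or awareness to determine if the participant should continue or discontinue study intervention". This also orders no interim hold.
- The referral to the product label at the end of Section 6.6.2 is for other dose modifications, not for events already listed.
- The Grade 2 non-hematologic row in Section 6.6.1 does order a hold, but of LY3475070 only and for non-immune-mediated events. It may help before an immune cause is suspected; it does not govern a suspected irAE.

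None of these settles the difference.

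**The case against.** The strongest reply is that the two texts can be followed together. To consider withholding is not permission to continue, and the Note contains no waiver. Its context is cautionary throughout: closer monitoring, specialist work-up and sponsor consultation. The table is also titled as guidelines, so calling its entries orders and any departure a breach goes further than the source. Finally, every suspected irAE of Grade 2 or above should reach the sponsor physician.

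Most of this stands. The Note was very likely meant to add caution, the table is probably the intended rule, and the consultation request is a real safeguard. It does not remove the mismatch. A site reading the Note alone would find the Grade 2 myocarditis hold presented as a judgment, and no sentence sends it back to the firmer entry in the table.

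A reader might also infer that all three toxicities named in the Note are in equal conflict with the table. The documents do not support that. For neurologic and ophthalmologic irAEs the table acts at Grade 2 only when the event persists, so the Note mainly extends caution to states that the table leaves open. The overlap at persistent Grade 2 is real but narrow. Nor is it sound to count conflicting states by splitting myocarditis into persistent and non-persistent Grade 2: the table makes no such split, and doing so counts one row twice.

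**Conclusion.** Wrong as written, and minor. Section 6.6.2 carries two instructions of different strength for Grade 2 myocarditis, with no statement of which prevails. The secondary overlap is persistent Grade 2 neurologic or ophthalmologic irAEs. There is no conflict at Grades 1, 3 or 4.

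The conclusion rests on two readings: that the myocarditis entry is meant as a required action because footnote d is not attached to it, and that the Note's Grade 2 wording covers myocarditis because it names it.

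A reader might infer that patients would be dosed through myocarditis, or that the recommended Phase 2 dose is affected. Neither follows. A site that asks the sponsor, as the Note requests, would have the case reviewed. The documents give no incidence for these events, so no patient count can be stated, and no effect on dose selection, endpoints or analyses is claimed.

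**What to change.** Make two edits to the Note in Section 6.6.2.

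1. Remove myocarditis from the clause on considering a hold at Grade 2, leaving neurologic and ophthalmologic irAEs there. Keep myocarditis in the clause on early hospitalization at Grade 3.
2. Add one sentence: *The table actions are minimum requirements and this Note does not relax them.*

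The first edit removes the direct mismatch. The second supplies the missing precedence rule and also covers persistent Grade 2 neurologic and ophthalmologic irAEs, while keeping the Note's added caution at other Grade 2 events.

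The cost is one sentence edited and one added, in the next amendment or in a clarification letter to sites.

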### **6.6.3. Other allowed dose interruption for pembrolizumab**

Pembrolizumab may be interrupted for situations other than treatment-related AEs such as medical / surgical events or logistical reasons not related to study therapy. Participants should be placed back on study therapy within 3 weeks of the scheduled interruption, unless otherwise discussed with the Sponsor. The reason for interruption should be documented in the patient's study record.

## **6.7. Intervention after the End of the Study**

The end of study definition is defined in Section 4.4. Investigators will continue to follow the SoA provided in Section 1.3 until notified by Lilly that end of study has occurred.

### **6.7.1. Treatment after Study Completion**

Study completion will occur following the final analysis of primary and secondary objectives, as determined by Lilly. Investigators will continue to follow the SoA (Section 1.3) for all patients until notified by Lilly that study completion has occurred.

#### **6.7.1.1. Continued Access**

Participants who are still on study intervention at the time of study completion may continue to receive study intervention if they are experiencing clinical benefit and no undue risks.

The continued access period will apply to this study only if at least 1 participant is still on study intervention when study completion occurs. Lilly will notify investigators when the continued access period begins.

If LY3475070 is discontinued, pembrolizumab may be continued alone for up to 2 years (35 cycles). Conversely, if pembrolizumab is discontinued, LY3475070 may be continued alone.

Participants are not required to sign a new ICF before treatment is provided during the continued access period; the initial ICF for this study includes continued access under this protocol.

The participant's continued access to study intervention will end when a criterion for discontinuation is met (Section 7). Continued access follow-up will begin when the participant and the investigator agree to discontinue study intervention and lasts approximately 90 days. Follow-up procedures will be performed as shown in the Continued Access SoA.

Participants who are in short-term follow-up when the continued access period begins will continue in short-term follow-up until the 90-day short-term follow-up visit is completed. Long-term follow-up does not apply.

Participants who are in long-term follow-up when the continued access period begins will be discontinued from long-term follow-up.

In all cases, no follow-up procedures will be performed for a participant who withdraws informed consent unless he or she has explicitly provided permission and consent.

## **7. Discontinuation of Study Intervention and Participant Discontinuation/Withdrawal**

The reasons for treatment and study discontinuation and dates of discontinuation will be collected for all patients.

Patients who discontinue during the study treatment period, whether or not they received study treatment, will have follow-up procedures performed as shown in the SoA (Section 1.3).

If a patient withdraws informed consent, he or she must not be contacted unless he or she has explicitly provided permission and consent. Lilly may continue to use previously collected medical research data prior to the withdrawal consistent with the original authorization.

